5.2 Selection of Study Population

Subjects will be screened to determine if they meet all of the inclusion criteria specified in Section 5.2.1 and none of the exclusion criteria specified in Section 5.2.2.

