- 9. Subject must agree to daily use of one of the following over-the-counter topical antiseptics on their HS lesions (excepting the post-surgical wound): chlorhexidine gluconate, triclosan, benzoyl peroxide, or dilute bleach with shower or bath throughout the entirety of the study;
- 10. Subject has a negative TB screening assessment (see test to be performed in paragraph below) and negative CXR (posterior-anterior [PA] and lateral view) at Screening. If the subject has evidence of a latent TB infection; the subject must initiate and complete a minimum of 12 weeks (or per local guidelines, whichever is longer) of an ongoing TB prophylaxis and have documented completion of a minimum of 4 weeks of TB prophylaxis prior to the Baseline visit (see Section 5.3.1) and should be evaluated by a physician experienced in the evaluation and treatment of TB patients before entering the trial;

- In patients treated with corticosteroids (equivalent to Prednisone 5 mg or above – with ongoing treatment or treatment within 1 month prior to TB screening), TB screening must be performed using a QuantiFERON-TB Gold In-tube test or equivalent.
 - In patients NOT treated with corticosteroids (equivalent to Prednisone 5 mg or above – with ongoing treatment or treatment within 1 month prior to TB screening), PPD or QuantiFERON-TB tests may be used.
11. Subject is judged to be in good general health, as determined by the Study Investigator based upon the results of a medical history, physical examination, laboratory profile, CXR and a 12-lead ECG performed during the Screening period and confirmed at the Baseline visit;
 12. Subject must be able and willing to self-administer subcutaneous (SC) injections or have a qualified person available to administer SC injections; and
 13. Subject must be able and willing to provide written informed consent and comply with the requirements of this study protocol.

Rationale for the Inclusion Criteria

- | | |
|--------|--|
| 1 – 6 | To select the appropriate subject population with adequate disease severity for the evaluation |
| 7 – 8 | The impact of adalimumab on fetal development has not been formally established |
| 9 – 12 | For the safety of the study subject |
| 13 | In accordance with harmonised Good Clinical Practice (GCP) |

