In the assessment of the CXR, a radiologist must specifically note the presence or absence of 1) calcified granulomas, 2) pleural scarring/thickening, and 3) signs of active TB. The Study Investigator will indicate the clinical significance of any findings and will sign and date the CXR report. If the CXR demonstrates changes suggestive of previous TB (e.g., calcified nodule, fibrotic scar, apical or basilar pleural thickening) or other findings that are clinically significant, the Study Investigator must contact the AbbVie Study Designated Physician before enrolling the subject.

TB Screening

In patients treated with corticosteroids (equivalent to Prednisone 5 mg or above – with ongoing treatment or treatment within 1 month prior to TB screening), an Interferon-Gamma Release Assay (IGRA; QuantiFERON-TB Gold In-Tube test or T-SPOT TB test) may be performed locally or by the central lab during the Screening Period for all subjects, including those with a prior history of Bacille Calmette-Guérin (BCG) administration.

In patients NOT treated with corticosteroids (equivalent to Prednisone 5 mg or above – with ongoing treatment or treatment within one month prior to TB screening), a PPD skin test (alternatively, also known as tuberculin skin test) must be placed, or an Interferon-Gamma Release Assay (IGRA; QuantiFERON-TB Gold In-Tube test or T-SPOT TB test)

may be performed locally or the central lab during the Screening Period for all subjects, including those with a prior history of Bacille Calmette-Guérin (BCG) administration.

If a subject had a negative PPD or IGRA test within 90 days prior to Screening, and all protocol required documentation is available, the test does not need to be repeated, provided nothing has changed in the subject's medical history to warrant a repeat test, and that in patients treated with corticosteroids (equivalent to Prednisone 5 mg or above – with ongoing treatment or treatment within 1 month prior to TB screening) the performed screening was an Interferon-Gamma Release Assay. These cases must be discussed with the AbbVie Study Designated Physician.

For the PPD test:

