The subject will be required to have the PPD skin test read by a licensed healthcare professional 48 to 72 hours after placement (or as per local guidelines), when the induration is maximal. An induration (not erythema) of 5 mm or greater will be considered as PPD positive, regardless of BCG status or local guidelines. The induration must be recorded in "mm," not as "positive" or "negative." The absence of induration should be recorded, as "0 mm," not "negative." *(If required by specific countries a two-step test may be performed per local guidelines. The result of the second test should be recorded.)*

A subject, who has had an ulcerating reaction to a PPD skin test in the past, as documented in the medical history source and eCRF, should not be re-exposed and should not be tested at Screening but will be considered PPD positive.

If there are study sites where the available testing materials are not accepted, the method must be submitted and approved by the AbbVie Study Designated Physician prior to use with study subjects.

If the PPD or the IGRA test is positive, the subject has a prior history of active or latent TB, or the results of a CXR are indicative of latent TB (see Section 5.3.1.1), the subject will be required to initiate and have taken at least 4 weeks (or per local guideline,

whichever is longer) of an ongoing course of Centers for Disease Control and Prevention (CDC)-recommended prophylaxis or prophylaxis per local guidelines prior to starting study drug therapy and should be evaluated by a physician experienced in the evaluation and treatment of TB patients before entering the trial. Subjects who have a documented completion of the CDC-recommended prophylaxis may be permitted to enroll. The Principle Investigator should contact the AbbVie Study Designated Physician to discuss enrollment of this potential subject.

In the event both a PPD test and an IGRA test are performed, the result of the IGRA test will supersede the result of the PPD test. If the IGRA test is performed and the result is indeterminate, the test should be repeated with a fresh blood sample or perform a PPD test. If the repeat IGRA test is also indeterminate, this should be considered a positive test result and TB prophylaxis should be initiated.

Newly initiated prophylactic treatment should be recorded on the concomitant medications page in the eCRF and in the source documents. Prior therapy should be recorded on the medical history page in the eCRF.

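### After an indeterminate IGRA, the TB screening procedure allows a skin test even in corticosteroid-treated subjects, for whom Inclusion Criterion 10 requires QuantiFERON or equivalent

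*Protocol*

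**What the plan says.** Inclusion Criterion 10 (Protocol Section 5.2.1, with the same rule in the Synopsis) divides subjects by corticosteroid exposure: a prednisone-equivalent of 5 mg or above, either ongoing or within the month before TB screening. For exposed subjects, "TB screening must be performed using a QuantiFERON-TB Gold In-tube test or equivalent". A PPD is listed as an option only for subjects not so exposed.

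The TB Screening text in Section 5.3.1.1 then gives the procedure:

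- **Exposed subjects:** an IGRA "may be performed locally or by the central lab during the Screening Period for all subjects".
- **Other subjects:** a PPD ("also known as tuberculin skin test) must be placed"), or an IGRA in its place.
- **90-day waiver:** a recent negative test can stand in for a new one, but for exposed subjects only if "the performed screening was an Interferon-Gamma Release Assay".
- **Both tests done:** "the result of the IGRA test will supersede the result of the PPD test".
- **Indeterminate IGRA:** "the test should be repeated with a fresh blood sample or perform a PPD test". Corticosteroid exposure is not mentioned.
- **Second indeterminate IGRA:** "If the repeat IGRA test is also indeterminate, this should be considered a positive test result and TB prophylaxis should be initiated".

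**The concern.** The protocol restricts the test type for corticosteroid-treated subjects twice, once in the eligibility criterion and once in the waiver. It drops the restriction at the fallback after an indeterminate IGRA, which looks like an oversight. The result decides whether latent TB is treated before a 160 mg loading dose of a drug for which Section 3.6 lists TB reactivation. A site that takes the PPD option also avoids the conservative rule on a second indeterminate IGRA, which applies only if the IGRA is repeated.

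**Working it through.** **Text comparison.** The rules that apply to a corticosteroid-treated subject are:

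| Place | Test accepted |
|---|---|
| Inclusion Criterion 10 | QuantiFERON or equivalent only |
| 90-day waiver, Section 5.3.1.1 | earlier IGRA only |
| Fallback after indeterminate IGRA, Section 5.3.1.1 | repeat IGRA, or PPD |

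**The two paths from an indeterminate first IGRA.**

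1. *Repeat the IGRA.* A negative result clears the subject, a positive one leads to prophylaxis, and a second indeterminate one is handled as positive.
2. *Perform a PPD.* An induration of 5 mm or more is positive and leads to prophylaxis. Below 5 mm the test is negative and no further step is stated. Waiver cases must be discussed with the Study Designated Physician, but no such contact is required here.

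The precedence sentence does not close path 2. If it let an indeterminate IGRA override a PPD, the PPD option in the sentence after it would have no effect for anyone.

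**Who is affected.** There are two groups:

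- Ongoing users at 5 to under 7.5 mg/day prednisone-equivalent, because Exclusion Criterion 6 and Section 5.2.3.3 bar 7.5 mg/day prednisone or more at Baseline.
- Subjects whose course stopped in the month before TB screening. For high-dose prednisone, Exclusion Criterion 6 bars only the 8 days before Baseline (Day -8 to Day -1). Appendix C places Screening between Day -30 and Day -7. Taking the month as 30 days:
  - Screening on Day -7: look-back Day -37 to Day -8, overlap 1 day, so 30 − 1 = 29 days stay eligible.
  - Screening on Day -30: look-back Day -60 to Day -31, overlap 0, so all 30 days stay eligible.

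**Size.** The documents give no counts. Every rate below is an assumption; 200 is the planned enrolment.

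| Step | Assumed rate | Low | High |
|---|---|---|---|
| Corticosteroid-treated | 2–10% | 200 × 0.02 = 4 | 200 × 0.10 = 20 |
| First IGRA indeterminate | 2–10% | 4 × 0.02 = 0.08 | 20 × 0.10 = 2 |
| PPD chosen over repeat IGRA | 50% | 0.08 × 0.5 = 0.04 | 2 × 0.5 = 1 |
| Latent TB among these | 1–10% | 0.04 × 0.01 = 0.0004 | 1 × 0.10 = 0.1 |

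The last row counts subjects who have latent infection, not those who are missed. A miss also needs a PPD reading under 5 mm. If that happens with probability q in infected subjects, the upper figure is 0.1 × q. With q = 0.5 (again an assumption) it is 0.05 subject.

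**The case against.** **Eligibility rules may already settle it.** Section 5.2 states "Subjects will be screened to determine if they meet all of the inclusion criteria", Section 5.3.1.1 requires the criteria to be checked at Screening and Baseline, and Section 7.0 makes entry without meeting them a reportable deviation. A site can satisfy both texts by repeating the IGRA, so they are not impossible to follow together. That much stands. But nothing says that Inclusion Criterion 10 governs the fallback. A site could reason that the first IGRA, although indeterminate, met the criterion and that the procedure governs what follows. If the sponsor disagreed, the site would have a deviation caused by following the written procedure.

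**A stronger reading of the word *may*.** A reader might infer that Section 5.3.1.1 makes the IGRA itself optional for corticosteroid-treated subjects, because it uses *may* where Inclusion Criterion 10 uses *must*. The documents do not support this. The word most naturally refers to the choice of local or central laboratory, that paragraph offers no other test, and the waiver insists on an IGRA for this group. The contrast with the *must* for the PPD in the other group is also weak, because that PPD can itself be replaced by an IGRA.

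**A stronger reading of the risk.** A reader might infer that a meaningful number of latent infections would be missed. The 5 mm cut-off applies regardless of BCG status or local guidelines. The two-view chest X-ray, the TB exposure history and Exclusion Criterion 18 are further safeguards. A subject with latent infection, a normal film and no known history would pass those three, but would still need a falsely negative PPD.

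**The fix has its own burden.** At the upper bound, 1 subject moves from PPD to repeat IGRA. If 20% of repeats were indeterminate (assumption), 1 × 0.20 = 0.2 subject would enter a prophylaxis course, against fewer than 0.1 missed infections avoided. This is fair: the counts alone do not show a net benefit. The case for the change is that it applies the protocol's own safety rule consistently.

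**Timing.** SAP version 3 is dated 12 August 2019 and precedes database lock, so screening may already be over. The documents do not give enrolment status.

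**Conclusion.** The inconsistency is real and confined to the indeterminate-result fallback. It is a low-priority patient-safety consistency point, not a statistical one. The estimate is 0.04 to 1 of 200 subjects screened on a PPD in place of a repeat IGRA, and below 0.1 of a subject as a missed latent infection. Both rest wholly on the assumed rates. That the protocol intends IGRA-only screening for this group is well supported by the criterion and the waiver. How any site would read the fallback is not known.

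**What to change.** In the TB Screening text of Section 5.3.1.1, replace the indeterminate-result sentence with:

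> If the IGRA is indeterminate, repeat it with a fresh blood sample; a PPD may be performed instead only in subjects not treated with corticosteroids as defined in Inclusion Criterion 10.

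Keep the rule that a second indeterminate IGRA counts as positive, and leave the precedence sentence as it is. Changing *may* to *must* in the paragraph on corticosteroid-treated subjects is optional tidying.

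**Cost.** No new test type or visit is needed, only a few repeat blood draws. Corticosteroid-treated subjects indeterminate twice should be evaluated by a TB-experienced physician and need at least 12 weeks of prophylaxis under Section 5.2.1, with at least 4 of those weeks before Baseline. Four weeks is 28 days, which leaves 30 − 28 = 2 days of the screening window, so re-screening and later entry are likely. A PPD would have cleared some of these subjects. Section 5.3.1.1 already prescribes prophylaxis when the repeat IGRA is indeterminate.

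If the change counts as a substantial amendment, Section 9.1 requires ethics approval before it is implemented, across 56 planned sites. It is best placed in the next amendment. Until then, if screening is still open, a memo to sites saying that Inclusion Criterion 10 governs the fallback is enough.

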5.3.2 Drug Concentration and Anti-Adalimumab Antibody Measurements

Blood samples for adalimumab and Anti-Adalimumab Antibody (AAA) assays will be collected by venipuncture at the designated study visits listed in [Appendix C](#).

5.3.2.1 Collection of Samples for Analysis

Blood samples for PK adalimumab analysis will be collected by venipuncture into appropriately labeled 6 mL evacuated serum collection tubes without gel separator at the designated study visits listed in [Appendix C](#) (i.e., at Baseline, and Weeks 4, 8, 12, 14, 15, 17, 20, and 24/Premature Discontinuation Visit if the subject discontinues prior to Week 24). All samples will be obtained immediately prior to study drug administration.

Blood samples for AAA will be split from the PK sample collection after centrifugation to isolate serum. Detailed information will be provided in the laboratory manual. Processing for AAA samples will be done at the designated study visits listed in [Appendix C](#) (i.e., at Baseline, and Weeks 4, 8, 12, 15, 20, and 24/Premature Discontinuation Visit if the subject discontinues prior to Week 24).

Collection of Samples for Adalimumab Analysis

A maximum of 8 samples are planned to be collected per subject for PK adalimumab analysis. The total number of PK adalimumab samples planned will not exceed 1600 (8 samples × 200 subjects) for the entire study. Sample calculations are based on the maximum number of subjects.

Collection of Samples for Anti-Adalimumab Antibody Analysis

A maximum of 7 samples are planned to be split from the PK sample collection. The total number of AAA samples planned will not exceed 1400 (7 samples × 200 subjects) for the entire study. Sample calculations are based on the maximum number of subjects.

5.3.2.2 Handling/Processing of Samples

Sufficient blood will be collected to provide approximately 3 mL serum from each sample. The blood will be allowed to clot for 30 minutes at room temperature prior to centrifugation as described in the laboratory manual. The time that each blood sample is collected will be recorded to the nearest minute in the source document and on the appropriate eCRF. Samples will be analysed under the supervision of the AbbVie Drug Analysis Department.

Additional detailed instructions for the handling and processing of samples will be provided from the central laboratory.

5.3.2.3 Disposition of Samples

AbbVie will not supply dry ice for this study. The frozen serum samples for the adalimumab PK and, where applicable, AAA assays will be packed in dry ice (pellet form) sufficient to last 3 days during transport and shipped from the study site to the Central Laboratory. The two splits of each sample set (i.e., adalimumab, AAA) will be shipped in separate shipments in case of transportation problems (i.e., customs delays, damage or loss of shipment) as defined by the Central Laboratory.

5.3.2.4 Measurement Methods

Serum concentrations of adalimumab will be determined using a validated assay methodology under the supervision of the AbbVie Drug Analysis Department.

Serum concentration of AAA will be determined using a validated assay methodology under the supervision of the AbbVie Drug Analysis Department.

5.3.3 Efficacy Variables

5.3.3.1 Primary Variable

The primary efficacy variable is the proportion of subjects achieving HiSCR at Week 12. HiSCR is defined as at least a 50% reduction in the AN count with no increase in abscess count and no increase in draining fistula count relative to baseline.

5.3.3.2 Secondary Variables

Ranked Secondary Efficacy Variables

The following secondary efficacy variable will be analysed according to the rank order as follows:

1. Proportion of subjects achieving HiSCR-es (defined as the HiSCR excluding the HS surgical site) at Week 12,
2. Proportion of subjects achieving HiSCR-es at Week 24,
3. Percent change in surface area of the HS surgical site from Baseline to Week 12, and
4. Proportion of subjects at Week 12 that require a less extensive surgery than the surgical plan (determined at Baseline) or no surgery as determined by the designated surgeon.

Other Efficacy Variables

Other efficacy variables to be analysed at each scheduled visit in Periods A and C, except for the ones included as the primary or ranked secondary variables that will be analysed for visits other than Weeks 12 and 24 include:

- Change from Baseline in CRP
- Proportion of subjects with DLQI = 0
- Proportion of subjects with DLQI = 0 or 1

- Change from Baseline in DLQI score
- Change from Baseline in EQ-5D index
- Change from Baseline in HS-PGA-SP
- Change from Baseline in HS PGIC
- Change from Baseline in HSIA
- Change from Baseline in HSSA-7d
- Change from Baseline in SF-12
- Change from Baseline in TSQM
- Change from Baseline in WPAI:SHP
- Proportion of subjects that experience a flare, defined as an at least 25% increase in AN count with a minimum increase of 2 relative to Baseline at each study visit, during Period A and during the study
- Proportion of subjects that experience at least 25% increase in each lesion type with a minimum increase of 2 relative to Baseline at each study visit, during Period A and during the study

5.3.4 Safety Variables

Adverse events, laboratory data, physical examinations, and vital signs will be collected, monitored, assessed, and recorded at the designated study visits listed in [Appendix C](#) and as described in [Section 6.0](#) and [Table 1](#).

5.3.5 Pharmacokinetic Variables

Adalimumab trough serum concentrations will be summarized at each time point using descriptive statistics. In addition, within subject comparison of adalimumab concentrations before and after surgery will be performed. Percentage of subjects that develop immunogenicity during the 24-week study duration will be calculated. The impact of immunogenicity development on adalimumab PK, efficacy, and safety will be evaluated through comparison of adalimumab concentrations, primary efficacy outcome, and incidence of AEs between AAA+ and AAA– subjects.

5.3.6 Exploratory Research Variables

Biomarker assessments may be used to assess and generate prognostic, predictive, pharmacodynamics, or surrogate biomarker signatures. These assessments may be explored in the context of HS or related conditions, and/or adalimumab or drugs of similar classes. The results from these analyses are exploratory in nature and may not be included with the clinical study report.

The sample may also be used to develop new therapies, research methods, and technologies. In addition, samples from this study may be banked for future use. Samples may then be used to validate putative biomarker signatures obtained from a prospective study, leading to the development of diagnostic tests.

5.4 Removal of Subjects from Therapy or Assessment

5.4.1 Discontinuation of Individual Subjects

A subject may withdraw from the study at any time. The Principle Investigator may discontinue any subject's participation for any reason, including an adverse event, safety concerns, or failure to comply with the protocol.

Subjects will be withdrawn from the study immediately if any one of the following occurs:

- Clinically significant abnormal laboratory result(s) or adverse event(s), as determined by the Study Investigator in consultation with the AbbVie Study Designated Physician;
 - The Study Investigator believes it is in the best interest of the subject;
 - The subject requests withdrawal from the study;
- Inclusion and exclusion criteria violation was noted after the subject started study drug, when continuation of the study drug would place the subject at risk as determined by the AbbVie Study Designated Physician (see Section 5.2 and Section 7.0);

- Introduction of prohibited medications or dosages when continuation of the study drug would place the subject at risk as determined by the AbbVie Study Designated Physician;
- Subject is non-compliant with TB prophylaxis;
- The subject develops tuberculosis, or any other significant or opportunistic infections;
- The subject becomes pregnant while on study drug;
- Subject has dysplasia of the gastrointestinal tract of a malignancy, except for localized non-melanoma skin cancer. Discontinuation for carcinoma in situ of the cervix is at the discretion of the Study Investigator;
- Subject is diagnosed with lupus-like syndrome, multiple sclerosis, or demyelinating disease;
- Subject is significantly non-compliant with study procedures that would put the subject at risk for continued participation in the trial, as determined by the Study Investigator, in consultation with the AbbVie Study Designated Physician.

If, during the course of study drug administration, the subject prematurely discontinues study drug use, the procedure outlined for the Premature Discontinuation Visit must be completed within 2 weeks of the last dose of study drug, and preferably prior to the initiation of another therapy. However, these procedures should not interfere with the initiation of any new treatments or therapeutic modalities that the Study Investigator thinks are necessary to treat the subject's condition. Following discontinuation of the study drug, the subject will be treated in accordance with the Study Investigator's best clinical judgment.

All attempts must be made to determine the date of the last dose of study drug and the primary reason for premature discontinuation. The information will be recorded on the appropriate eCRF page.

For subjects who are considered lost to follow-up, reasonable attempts must be made to obtain information on the final status of the subject. At a minimum, two telephone calls must be made and one certified letter must be sent.

